## 7.1 Study Rationale

Since 2007 there has been only 1 approved systemic medication (sorafenib) for patients with uHCC. Because of this fact in the treatment landscape, studies that evaluated second line treatment of HCC required prior sorafenib as first line therapy. Therefore, the currently approved second line medications (regorafenib and nivolumab) were studied as subsequent sequential therapies to sorafenib. Results from the phase 3 REFLECT study (Study 304) demonstrated the treatment effect of lenvatinib on OS, which was statistically confirmed by non-inferiority to sorafenib for first-line treatment for patients with uHCC. Therefore, it is important to address unmet medical need for data for safety and efficacy on the subsequent sequential therapies after 1st line therapy with lenvatinib in uHCC patients.

The safety and efficacy of lenvatinib in first line uHCC has been established in the large Phase 3 international REFLECT study. This has led to the approval of lenvatinib as first line treatment in uHCC in Japan, EU and in the US. In the REFLECT study, upon progression with first line lenvatinib, 32.6% of patients received subsequent anticancer medications. The information on safety of the subsequent medications after lenvatinib was not captured in the REFLECT study, since patients on lenvatinib were followed post-progression only for OS. Therefore, the objective of study E7080-M001-222 is to capture the safety and tolerability of the subsequent sequential therapy after first-line lenvatinib in patients with uHCC.

The survival follow-up from Study 304 has shown some preliminary information of subsequent treatment following the first-line lenvatinib treatment in HCC subjects during the study period (01 Mar 2013 to 13 Nov 2016). During survival follow-up in Study 304, the percentage of subjects receiving post-treatment anticancer medications (not given for a procedure) in the lenvatinib arm compared with sorafenib arm was 32.6% vs 38.7%, respectively. Sorafenib was the most common anticancer agent given to lenvatinib-treated subjects during survival follow-up, taken by 25.3% of subjects; 11.8% of sorafenib-treated subjects restarted or continued sorafenib during survival follow-up. The percentage of subjects who took investigational anticancer drugs during survival follow-up in the lenvatinib arm compared with the sorafenib arm was 3.1% vs 9.5%, respectively. These investigational agents were mostly administered within clinical trials (eg, regorafenib, cabozantinib), which

required failure of sorafenib therapy as an entry criteria, thus precluding enrollment of lenvatinib-treated subjects in these studies ([Study E7080-G000-304 Clinical Study Report, 2017](#)).

This is a single-arm, open-label, multicenter, Phase 2 study to evaluate the safety and efficacy of subsequent systemic treatment of physician choice (TPC) (commercially available) following first-line lenvatinib treatment for uHCC.

The primary objective of the study is to evaluate the safety and tolerability of subsequent systemic TPC following first-line lenvatinib treatment in uHCC subjects. The secondary objectives include evaluation of OS in uHCC subjects treated with lenvatinib as first-line treatment followed by TPC, and evaluation of PFS and TTP of subsequent systemic TPC starting from the first dose of first-line lenvatinib treatment.

Approximately 100 subjects will be enrolled to first-line treatment with lenvatinib. Subjects with Child-Pugh A will be included in this study. Starting dose of lenvatinib will be based on baseline BW: 12 mg QD or 8 mg QD will be orally administered for subjects' BW  $\geq 60$  kg or  $< 60$  kg, respectively.

## **8 STUDY OBJECTIVES**

### **8.1 Primary Objective**

- To assess the safety and tolerability of subsequent systemic TPC following the first-line lenvatinib treatment in uHCC subjects.

### **8.2 Secondary Objectives**

- To evaluate OS in uHCC subjects treated with lenvatinib as the first-line treatment followed by systemic TPC
- To evaluate PFS and TTP of subsequent systemic TPC starting from the first dose of first-line lenvatinib treatment using modified RECIST (mRECIST)
- To evaluate OS by subgroups of systemic TPC

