### **Number of Subjects**

Approximately 100 subjects with uHCC will be enrolled to the first-line treatment of lenvatinib.

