### **Analysis Sets**

**Safety Analysis Set (Full Analysis Set)** is the group of subjects who received at least 1 dose of the lenvatinib treatment. This will be the analysis set for all safety and efficacy evaluations.

**The Pharmacodynamic Analysis Set** is all the subjects who have received at least 1 dose of lenvatinib and had sufficient pharmacodynamic data to derive at least 1 pharmacodynamic measurement and with documented dosing history.

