##### 9.7.1.1.2 SECONDARY ENDPOINTS

- Overall survival (OS), measured from the date of first dose of study treatment until date of death from any cause. Subjects who are lost to follow-up will be censored at the last date the subject was known to be alive, and subjects who remain alive will be censored at the time of data cutoff.
- Progression-free survival (PFS), defined as the time from the date of first dose of first-line lenvatinib treatment to the date of first documentation of disease progression, or date of death, during the subsequent systemic TPC, whichever occurs first.
- Time to progression (TTP), defined as the time from the date of first dose of first-line lenvatinib treatment to the date of first documentation of disease progression during subsequent systemic TPC.

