#### 9.7.1.2 Definitions of Analysis Sets

The **Safety Analysis Set (Full Analysis Set)** is the group of subjects who received at least 1 dose of study drug. This will be the analysis set for all safety and efficacy evaluations.

The **Pharmacodynamic Analysis Set** is all the subjects who have received at least 1 dose of lenvatinib and had sufficient pharmacodynamic data to derive at least 1 pharmacodynamic measurement and with documented dosing history.

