#### 9.7.1.6 Efficacy Analyses

Efficacy analyses will be performed based on the Safety Analysis Set.

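### Read literally, the OS objective concerns subjects who received TPC after lenvatinib, but the protocol's OS analysis covers all lenvatinib-treated subjects and sets no time origin for OS in TPC recipients or subgroups

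*Combined protocol and SAP*

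**What the plan says.** - **Objective.** Section 8.2 (also the synopsis and Section 7.1) sets out: "To evaluate OS in uHCC subjects treated with lenvatinib as the first-line treatment followed by systemic TPC". A further secondary objective in 8.2 is OS by TPC subgroup.
- **Endpoint.** Section 9.7.1.1.2: "Overall survival (OS), measured from the date of first dose of study treatment until date of death from any cause". Starting TPC is not a condition.
- **Analysis set.** The synopsis defines the Safety (Full) Analysis Set as "the group of subjects who received at least 1 dose of the lenvatinib treatment". Section 9.7.1.2 says study drug instead of lenvatinib, and adds: "This will be the analysis set for all safety and efficacy evaluations". Treatment starts with lenvatinib, so both definitions take in every lenvatinib-treated subject.
- **Analysis.** Section 9.7.1.6: "Efficacy analyses will be performed based on the Safety Analysis Set". For OS it gives a median, probabilities at selected times, 95% confidence intervals and Kaplan-Meier curves.
- **Subjects without TPC.** Under Sections 9.1.2.2 and 9.1.2.3, subjects judged unsuitable for systemic TPC go straight to survival follow-up, so their deaths count in OS.
- **Numbers.** The synopsis states: "Approximately 100 subjects with uHCC will be enrolled to the first-line treatment of lenvatinib". Section 9.7.2 assumes that more than half receive TPC, and Table 4 runs from 100% down to 50%. Section 7.1 reports that in Study 304 the share given later anticancer medication "in the lenvatinib arm compared with sorafenib arm was 32.6% vs 38.7%, respectively".

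**The concern.** The objective describes subjects by a treatment they go on to receive. The analysis describes them by the treatment they start with. Anyone who dies on lenvatinib, or is never suitable for TPC, is outside the first group and inside the second. Section 9.7 defines no TPC-treated set, no OS clock starting at TPC and no landmark analysis.

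Two things are at stake. First, Section 7.1 justifies the trial by the lack of safety and efficacy data on therapy after lenvatinib, and whole-cohort OS does not isolate that. Reported under the wording of objective 8.2, it could be taken for survival in TPC recipients. Second, OS by TPC subgroup has no method in Section 9.7.1.6. The only OS clock on offer starts at first lenvatinib dose. If subjects are then grouped by the TPC they later received, the time between first lenvatinib dose and TPC start is immortal: nobody who died in it can belong to any group.

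**Working it through.** **Step 1. Reproduce the plan's own figure.** Inputs from Section 9.7.2: Grade 3 or higher TEAE rate 75%, 100 subjects enrolled, 100% to 50% receiving TPC. Formula: half width = 1.96 × √(0.75 × 0.25 / n), with n the number of TPC recipients.

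| TPC recipients, n | Computed half width | Table 4 |
|---|---|---|
| 100 | 8.487% | 8.5% |
| 90 | 8.946% | 8.9% |
| 80 | 9.489% | 9.5% |
| 70 | 10.144% | 10.1% |
| 60 | 10.957% | 11% |
| 50 | 12.002% | 12% |

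All six rows agree after rounding, and only with TPC recipients as the denominator; with n fixed at 100, every row would be 8.5%. For the precision of the safety rate, then, the protocol treats TPC recipients as a distinct and possibly much smaller population. For OS it does not.

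**Step 2. Subjects in the OS set without TPC.** Formula: 100 × (1 − uptake).

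- Uptake 100%: 100 × (1 − 1.00) = 0.
- Uptake 50%: 100 × (1 − 0.50) = 50. The assumption is more than 50%, so the plan's range is 0 to just under 50.
- Uptake 32.6% (Study 304): 100 × (1 − 0.326) = 67.4, about 67, leaving about 33 TPC recipients.

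**Step 3. What the stated clock does in TPC recipients.** The protocol gives no OS assumption, so this step is an illustration. Assume:

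- exponential survival with median M from first lenvatinib dose;
- no effect of TPC on survival;
- every subject alive at time T starts TPC at T. Take T as 6 to 8 months, the protocol's estimate of lenvatinib duration (synopsis, Duration of Treatment; Section 9.4.1.1).

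Exponential survival has no memory, so subjects alive at T have a median of M still to come. Counted from first lenvatinib dose, the median among TPC starters is T + M.

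| M, months | Alive at T = 6 to T = 8: 0.5^(T/M) | Median from first lenvatinib dose, TPC starters |
|---|---|---|
| 10 | 0.660 to 0.574 | 16 to 18 |
| 12 | 0.707 to 0.630 | 18 to 20 |
| 14 | 0.743 to 0.673 | 20 to 22 |

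With a true median of 12 months and a TPC that does nothing, TPC recipients would show 18 to 20 months. The excess is T, the survival needed to enter the group. Counted from TPC start, the median in this model is 12 months and the excess is gone.

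**The case against.** The strongest defence is that the analysis matches the design. Section 9.4.3 assigns every eligible subject to lenvatinib and then TPC, and Sections 9.1 and 9.1.2.2 present TPC as the default next step. On that reading the sequence is the assigned strategy, and OS in all treated subjects from first lenvatinib dose estimates it without selecting on later events. This stands. A reader might infer that the whole-cohort OS is invalid; the documents do not support that.

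Other points also carry weight:

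- A reader might infer that the trial plans no OS by TPC at all. But Section 8.2 lists OS by TPC subgroup, and Sections 9.7 and 9.7.1 leave details to a separate SAP that is not among the documents. What can be said is that the protocol gives no method or time origin for it.
- The Study 304 rate is a weak guide. It covers later anticancer medication in general, including investigational drugs, over 2013 to 2016. Section 7.1 notes that lenvatinib subjects were shut out of trials requiring sorafenib failure, and Section 7 calls the second-line approvals recent.
- OS from first TPC dose leaves out the lenvatinib period, and the protocol times PFS and TTP from first lenvatinib dose. It therefore cannot by itself be the answer to objective 8.2.
- OS here is secondary and descriptive, in a single arm, with no test. The primary endpoint is untouched.

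The defence does not supply a TPC-treated set, a method for the subgroup objective, or protection against survivor bias if the stated clock is used there.

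**Conclusion.** The mismatch holds on a literal reading: objective 8.2 names subjects who received TPC after lenvatinib, and the protocol's OS analysis is for everyone who received lenvatinib. The planned analysis is sound for the assigned strategy but does not give survival in TPC recipients.

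The gap is 0 to just under 50 of 100 subjects over the plan's own range, and about 67 if uptake matched Study 304. A reader might infer that half or two thirds of the OS cohort will in fact receive no TPC. The documents do not support that: the first is the edge of a planning range and the second a weak proxy. The mismatch itself depends on neither figure.

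The more practical risk is the undefined subgroup analysis. Using the first-lenvatinib-dose clock in TPC recipients or subgroups biases OS upward. In the illustration the bias is 6 to 8 months, which rests on exponential survival, no TPC effect and a common TPC start time; the direction of the bias does not need those assumptions. All of this is a statement about the protocol, since the separate SAP may already deal with it.

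**What to change.** Before database lock, in the SAP or by amendment:

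1. Keep OS in all lenvatinib-treated subjects from first lenvatinib dose. Label it as OS under a strategy of starting lenvatinib, with TPC if appropriate, and say in objective 8.2 that this is what is meant. Name lenvatinib as the defining dose in Sections 9.7.1.1.2 and 9.7.1.2, as the synopsis does for the analysis set, because Section 9.4.2.4 also calls the Period 2 treatment study drug.
2. Define a TPC-treated set: subjects with at least one TPC dose.
3. Add a supplementary, descriptive OS from first TPC dose in that set, with Kaplan-Meier median and 95% confidence interval, stated as conditional on reaching TPC.
4. Use TPC start as the origin for OS by TPC subgroup, and put the method in Section 9.7.1.6.
5. If OS of the full sequence from first lenvatinib dose is wanted in TPC recipients, use left truncation at TPC start, so that subjects enter the risk set only then. Early risk sets may be small, and the start of the curve correspondingly unstable.

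The cost is low: one more Kaplan-Meier analysis, using treatment and survival dates the protocol already collects. The TPC-treated estimate has fewer subjects and a wider interval. As a rough guide, if the same fraction die in each set, the width grows by about √(100/50) = 1.41 at 50% uptake. Subjects who reach TPC are also a selected group, so the result should not be read as an effect of TPC.

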##### **9.1.1.2 Baseline Period/Visit**

Baseline assessments can be performed on Day -1 or prior to the start of study treatment on Cycle 1 Day 1. The purpose of the Baseline Visit is to confirm protocol eligibility and

disease characteristics, as specified in the inclusion/exclusion criteria (as detailed in [Section 9.3.1](#) and [Section 9.3.2](#)).

The screening assessment can serve as the baseline assessment, if performed within 72 hours before the first dose of study treatment. If the screening physical examination is performed  $>7$  days prior Cycle 1 Day 1, it must be repeated at the Baseline Visit. Laboratory tests and a pregnancy test (for female subjects of childbearing potential) may be performed up to 72 hours before the first dose of study treatment.

Subjects who complete the baseline assessment and meet the criteria for inclusion/exclusion ([Sections 9.3.1](#) and [9.3.2](#)) will begin the treatment phase. Results of baseline assessments must be obtained prior to the first dose of study treatment (Cycle 1 Day 1).

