#### 9.1.2.1 Lenvatinib Treatment Period (Treatment Period 1)

Lenvatinib Treatment Period for each subject will begin with the administration of first dose of lenvatinib on Cycle 1 Day 1 and will consist of administration of lenvatinib in 28-day treatment cycles. Treatment Period 1 will continue until completion of the lenvatinib Off-Treatment Visit that will occur within 30 days after the final administration of lenvatinib.

Lenvatinib treatment cycles will be counted continuously regardless of dose interruptions. Subjects will undergo safety and efficacy assessments as defined in the Schedule of Procedures/Assessments ([Table 3](#)). Subjects will continue to receive study treatment until disease progression, development of unacceptable toxicity, subject request, withdrawal of consent, or study termination by the sponsor.

Subjects will be permitted to continue lenvatinib treatment beyond mRECIST defined disease progression as long as the treating investigator considers that there is clinical benefit and, the subject is tolerating study treatment. The assessment of clinical benefit should take into account whether the subject is clinically deteriorating and unlikely to receive further benefit from continued treatment. All decisions to continue treatment beyond initial progression must be discussed with the Eisai Medical Monitor. Subjects will discontinue study treatment upon evidence of further progression and/or loss of clinical benefit, as judged by the investigator.

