#### 9.1.2.2 Subsequent Treatment Period (TPC Period, Treatment Period 2)

The subsequent TPC period will begin upon the completion of the lenvatinib Off-Treatment Visit in first-line treatment of lenvatinib. Subjects will be treated with commercially available systemic TPC for uHCC. The first treatment of a single agent or combination of multiple drugs after lenvatinib treatment will be considered as the subsequent TPC. Locoregional therapies (ie, chemoembolization/radioembolization, etc) procedures will not

be considered as a second line treatment following lenvatinib. If the investigator deems a subject inappropriate for commercially available systemic TPC as the subsequent treatment following lenvatinib, subjects will be followed in the survival Follow-Up period. All treatment following lenvatinib will be captured in the case report form. Data will be collected from the start of TPC, then at intervals as indicated in Schedule of Procedures/Assessments ([Table 3](#)).

Subjects starting subsequent TPC  $\geq$ 8 weeks after lenvatinib off-treatment visit may be considered after discussion with sponsor.

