## 9.4 Treatments

### 9.4.1 Treatments Administered

#### 9.4.1.1 Test Drug: Lenvatinib

Lenvatinib capsules will be administered orally, QD in continuous 28-day cycles. The starting dose of lenvatinib will be based on the subject's baseline BW as follows:

- BW  $\geq$ 60 kg — Lenvatinib 12 mg (taken as three 4-mg capsules) QD.
- BW  $<$ 60 kg — Lenvatinib 8 mg (taken as two 4-mg capsules) QD.

Study medication should be taken at approximately the same time each day in a fasting state or following a meal.

If a dose is missed and cannot be taken within 12 hours, then that dose should be skipped and the next dose should be taken at the usual time of administration.

Lenvatinib treatment will continue until disease progression, development of unacceptable toxicity, subject requests to discontinue, withdrawal of consent, or termination of the study

by the sponsor. The duration of lenvatinib treatment for each subject is estimated to be 6 to 8 months.

If holidays or personal schedules make administration impossible on the scheduled days, then administration should be resumed as soon as possible.

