- z: SAEs irrespective of relationship to study treatment must be reported as soon as possible but not later than 1 business day. AEs will be recorded for 28 days after last dose of lenvatinib treatment if subjects do not enter TPC period, or for 8 weeks after the start of TPC period. During treatment interruption due to AEs, repeat AE assessment at least every 7 days (until restarting administration). SAE information should be collected for 8 weeks after the start of the TPC, or for at least 28 days after the last dose of lenvatinib/TPC if subjects do not continue into the TPC period or do not stay in the TPC period for the 8 weeks of safety monitoring.
- aa: After week 16, only tumor assessment and TPC dose information will be collected until the end of TPC (disease progression, development of unacceptable toxicity, subject request, withdrawal of consent, or study termination by the sponsor).

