### OS

The median OS and the cumulative probability of OS at selected time points will be calculated and presented with 2-sided 95% CIs. The selected time points will depend on the

OS times that are observed during the study and will be specified in the SAP. Kaplan-Meier (KM) estimates of OS will be plotted over time.

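### OS by TPC subgroup has no origin other than first lenvatinib dose, so each subgroup curve includes lead-in time in which no member can die

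*Combined protocol and SAP*

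**What the plan says.** Section 8.2 and the synopsis list three secondary objectives on efficacy. The third is "To evaluate OS by subgroups of systemic TPC".

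OS is defined once, in the same words in the synopsis and in Section 9.7.1.1.2: "measured from the date of first dose of study treatment until date of death from any cause". Two other sections fix what that first dose is. Section 9.1.1.2 equates it with Cycle 1 Day 1: "Results of baseline assessments must be obtained prior to the first dose of study treatment (Cycle 1 Day 1". Section 9.1.2.1 says what is given on that day: "Lenvatinib Treatment Period for each subject will begin with the administration of first dose of lenvatinib on Cycle 1 Day 1". The synopsis also lists TPC under its study treatments, but on either reading the first dose is lenvatinib.

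Under Sections 9.1.2.2 and 9.4.1.2, the TPC is the first systemic treatment after lenvatinib, in a period that opens once the lenvatinib Off-Treatment Visit is complete. Subjects judged unsuitable for systemic TPC go to survival follow-up instead.

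For the OS analysis, Section 9.7.1.6 says "The median OS and the cumulative probability of OS at selected time points will be calculated", with 95% confidence intervals and Kaplan-Meier plots, on the Safety Analysis Set. It does not mention the TPC subgroups, an origin at TPC start, a landmark or delayed entry. Sections 9.7 and 9.7.1 leave further detail to a separate SAP.

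**The concern.** Membership of a TPC subgroup is settled by something that happens months after the OS clock starts. To be counted under a given agent, a subject must have stopped lenvatinib, survived to the start of that agent and been considered fit for it. All of that time then counts as survival in the subgroup's curve, although no member could have died in it. This is immortal time.

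The study exists to supply safety and efficacy information on treatment after lenvatinib (Sections 7.1 and 9.2), and agent-specific OS is where a reader will look for it. A median from the lenvatinib origin combines three components: time on lenvatinib, the gap to TPC, and survival after TPC start. Only the third concerns the TPC. The first two vary between subjects, because lenvatinib may stop for progression, toxicity or subject request, and TPC may begin 8 or more "weeks after lenvatinib off-treatment visit may be considered after discussion with sponsor".

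**Working it through.** **The plan's own figure.** The protocol states no figure for OS or for OS by subgroup. Its only precision statement (Section 9.7.2, Table 4) concerns the rate of Grade 3 or higher events. It reproduces (1.96 × √(0.75 × 0.25 / 50) = 12.0%) but has no bearing here.

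**Step 1: the structural point.** For a member, let W be the time from first lenvatinib dose to first TPC dose, and R the survival time after first TPC dose. OS under the stated definition is W + R. Membership requires being alive at W, so no member can die between 0 and W. This needs no assumed number.

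**Step 2: inputs for size.**
- Lenvatinib duration of 6 to 8 months: "The duration of lenvatinib treatment for each subject is estimated to be 6 to 8" months (Section 9.4.1.1). This is a planning estimate, not a minimum.
- Off-Treatment Visit up to 30 days after the last lenvatinib dose (Section 9.1.2.1), then TPC, with starts at 8 weeks or later open to discussion with the sponsor (Section 9.1.2.2).
- Median survival after TPC start of 7.8 months. This is an assumption, borrowed from the placebo arm of the second-line regorafenib trial in Section 7, whose subjects had prior sorafenib, not lenvatinib.

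**Step 3: medians with the same W for every member.** Median from lenvatinib = W + median of R.

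| W (months) | Median from TPC start | Median from first lenvatinib dose | W as share of the latter |
|---|---|---|---|
| 6 | 7.8 | 13.8 | 6 / 13.8 = 43% |
| 8 | 7.8 | 15.8 | 8 / 15.8 = 51% |

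Adding 30 days and 8 weeks (86 days / 30.44 = 2.8 months) makes W 8.8 to 10.8, and the medians become 16.6 to 18.6. The shift equals W whatever median is assumed after TPC start.

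**Step 4: time-point probabilities.** Take W = 6 and exponential R with median 7.8. At month 6 the subgroup's OS probability from the lenvatinib origin is 100% by construction; from TPC start it is 0.5^(6/7.8) = 59%. At month 12 the figures are 59% from the lenvatinib origin and 0.5^(12/7.8) = 34% from TPC start.

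**Step 5: variable W.** W will differ between subjects, and the shift then no longer equals the median of W. In simulation with exponential W (medians 6 and 8 months) and exponential R (median 10.6 months, the regorafenib arm in Section 7), the medians from lenvatinib were 19.8 and 22.4 months. The shifts are 9.2 and 11.8 months, so with a right-skewed lead-in the 6 to 8 months of Step 3 is an understatement.

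**Step 6: between agents.** If two agents have the same survival after TPC start but W is 6 months for one and 8 for the other, their medians from lenvatinib are 13.8 and 15.8; from TPC start both are 7.8. Now assume 25 deaths per subgroup (half of 50 recipients, no censoring) and exponential R. The standard error of one median is about (7.8 / ln 2) / √25 = 2.25 months, and of a difference √2 × 2.25 = 3.2 months. A 2-month artefact between agents is within sampling error. The shift of every subgroup median is the firmer result.

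**The case against.** The best defence is that the lenvatinib origin is deliberate. The first secondary objective is OS in subjects given lenvatinib and then TPC, and Section 8.2 anchors even PFS and TTP of the TPC at the first lenvatinib dose. OS by TPC subgroup can then mean survival of each lenvatinib-then-agent sequence, which is a legitimate quantity. This stands in part: the origin is acceptable for that purpose, provided the result is stated to be conditional on reaching TPC. The protocol does not state that condition, and without it a reader will take the median as survival on the agent.

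A second defence is that the error is inferred. The protocol writes no subgroup analysis, and the separate SAP could set another origin. That also stands, and limits the claim to the protocol. An SAP that follows the protocol will nevertheless inherit its only OS definition.

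Three stronger readings are tempting, and the documents do not support them:
- **A biased comparison of TPC recipients with non-recipients is planned.** None is. Every TPC subgroup consists of recipients, so the usual false survival advantage of treated over untreated does not arise in a planned analysis.
- **Agents will be wrongly ranked.** This needs lead-in times that differ by agent. No section suggests that they will, and no test between agents is planned.
- **OS from first lenvatinib dose is wrong altogether.** It is the natural definition for the whole treated set.

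**Conclusion.** The point holds in this form. On the protocol's only OS definition, each TPC subgroup curve carries a lead-in free of deaths, so its median and time-point probabilities do not describe survival on or after the TPC. That much follows from the definitions alone.

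The size depends on assumptions. It is 6 to 8 months on every subgroup median if TPC follows directly after the planned lenvatinib duration. It is more with a gap or a skewed lead-in, and less if lenvatinib stops early. Distortion between agents is possible but not shown.

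The analysis is a descriptive secondary one in a study whose primary endpoint and sample size concern safety. The harm is therefore to interpretation, not to error rates or power. The change should be made, but it does not put the main purpose of the study at risk.

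**What to change.** In Sections 9.7.1.1.2 and 9.7.1.6, and in the SAP:

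1. Define OS by TPC subgroup from the date of first TPC dose.
2. Keep OS from first lenvatinib dose for the whole treated set. If it is also shown by TPC subgroup, caption it as survival of the lenvatinib-then-TPC sequence, conditional on reaching TPC.
3. Label subgroup results descriptive, and tabulate lenvatinib duration and gap to TPC by subgroup. Moving the origin removes the immortal time but not confounding by lenvatinib duration or by choice of agent.

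The cost is one definition, one analysis sentence and the matching SAP text. No new data are needed: Section 9.1.2.2 has data collected from the start of TPC, and Table 3 continues dosing records to its end ("After week 16, only tumor assessment and TPC dose information will be collected until the end of TPC"). The downside is that subgroup medians will be shorter and not directly comparable with whole-cohort OS, which a table footnote should say.
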